Duration administration	of	Sub-Study 1 at home quarantine Arm 1: HCQ 2 weeks 400 mg bid; Arm 2: Placebo 2 pills bid for 2 weeks; crossover allowed upon disease progression or lack of clearance of virus Sub-Study 3 Healthcare worker prophylaxis. Arm 1: HCQ 600 mg qd for 2 months versus Arm 2: Placebo 3 pills qd for 2 months; crossover from placebo to HCQ is allowed upon disease progression/ virus confirmation
Study design		1:1 randomization in each cohort between the arms 1 and 2
Duration of trial		Approximately 1 year

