5.0 RANDOMIZATION

After all applicable screening assessments have been performed, participants who have met all inclusion criteria and none of the exclusion criteria will be centrally, randomly allocated to one of the two groups in each sub-study. Randomization will be done using computer generated randomization numbers. Treatment **should start within 3 working days after randomization.** Once the order for study drug arrives at the

The PATCH Trial

pharmacy and the participant is randomized only the pharmacist is aware of the assignment of HCQ versus placebo in the double blind sub-studies (1 and 3).

Blinding: Sub-Study 1 and 3 will have a double-blind placebo controlled design.

Unblinding: Sub-Study1: If a participant progresses with symptoms of COVID-19 based on the assessment scale outlined below an appropriately delegated and credentialed study team member will review the case with a clinical investigator who will sign off on the need to un-blind the participant. If the participant was on placebo and continues to have symptoms, then he/she will be allowed to crossover to the HCQ dosing. The EM van will deliver the HCQ to the participant. If the patient was on HCQ then HCQ will be stopped and the patient will be asked to seek the advice of their primary care doctor or go to the emergency room if symptoms are becoming more worrisome. Participants who have progressive symptoms and are subsequently hospitalized due to COVID-19 will be unblinded but not be crossed over to receive HCQ at the time of unblinding.

Sub-Study 3: If the participant at any time has worsening symptoms consistent with new onset of COVID-19 disease a COVID-19 PCR test is performed. Antibody tests alone will not be used to make decisions for this study. If the PCR test is positive for SARS-CoV-2 an appropriately delegated and credentialed study team member will contact IDS and the pharmacist will indicate which arm the participant was assigned. If the participant was assigned to placebo and wishes to cross over to HCQ, IDS will provide HCQ at the same dose as the Sub-Study 3 HCQ arm and IDS will ship the HCQ to the participant. If the participant was assigned to HCQ then the participant will be advised to seek the advice of their personal physician or go to the emergency room if symptoms are becoming more worrisome.

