3. Live attenuated vaccines during the study
4. Herbal and natural remedies must be avoided

7.4 Duration of Protocol Treatment and Follow-up.

Sub-Study 1 duration of treatment is up to 2 weeks or at the time of release from quarantine. HCQ will be stopped in all patients at the time of release from quarantine

Sub-Study 3 duration of treatment is 2 months with assay to assess SARS CoV2 every 2 weeks.

7.5 Crossover from Control to HCQ arm. For Sub-Study 1 all participants are un-blinded upon symptom progression (see response assessment below) after at least 7 days of treatment or upon hospitalization if this occurs prior to 7 days of treatment. If the participant was assigned to placebo, he/she has the option to crossover to receive HCQ 400 mg po bid for up to 2 weeks or until criteria for release from quarantine are met (See 1.0 primary endpoint). During these 2 weeks of HCQ treatment, the patient will continue to complete the daily diary. An appropriately delegated study team member will call the patient daily to assess worsening symptoms and AEs. Patients who are not improving will be sent to the hospital for further care. Participants who have progressive symptoms and are subsequently hospitalized as related to COVID-19 will not be crossed over to receive HCQ at the time of unblinding.

In sub-study 3 participants who have worsening symptoms as defined as fever, significantly worsening cough, shortness of breath or hypoxia but do not require hospitalization and tests positive for SARS-CoV2 virus are allowed to cross over to receive HCQ, or treated with an alternative therapy per physician's choice. Once the positive test returns, the CRC will email IDS to initiate unblinding IDS will inform the CRC and clinical investigator if the patient was on placebo. The clinical investigator will contact the subject and inform them that if they were on placebo they would have the option of being treated with HCQ 600 mg qd. If the patient agrees, the clinical investigator will place the order in EPIC for HCQ 600 mg qd through IDS. Drug will be delivered to the patient's home. During these 2 weeks of HCQ 600 mg po qd treatment, clinical investigators will call the patient every 1-3 days depending on the severity of symptoms to assess worsening symptoms and AEs. Patients who are not improving will be sent to the hospital for further care.

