Anterior nares specimen: Participants will self-collect these samples on day 0 (start date for HCQ) before the HCQ is taken, Day 3, and day 7

The PATCH Trial

Foam swab provided: Puritan 6" Sterile Standard Foam Swab w/ Polystyrene Handle (SKU # 25-1506 1PF)

Collection instructions: Use a single foam swab for collecting specimens from both nares. Insert foam swab into 1 nostril straight back (not upwards). Once the swab is in place, rotate it in a circular motion 2 times and keep it in place for 15 seconds. Repeat this step for the second nostril using the same swab. Remove foam swab and insert the swab into the supplied tube.

Storage instructions: The collected swab should be placed into the bag marked "Nares swabs collected" and the date and time of the swab collection should be filled out Redcap. The "Collected" bag is then placed in the freezer in the same sealed container as the oral fluid.

Specimen stability for all specimen types for all tests is now as follows:

Room temperature: 5 days

Refrigerated (2 °C–8 °C): 5 days

Frozen (-20 °C): 7 days

Frozen (-70 °C): Acceptable

Specimen pickup: At the end of quarantine, or end of study procedures, the nares swabs will be collected. And shipped to Quest Diagnostics to assess viral titers. Cold packs or dry ice should be used during collection and cold packs should be used during shipping to Quest.

Pill diary: When the participant is released from quarantine the electronic pill diary must be submitted electronically.

Monitoring co-inhabitants: Appropriately delegated and credentialed study team members (as example: Clinical Research Coordinator) will ask the participant about the status of co-inhabitants daily to 14 days after the quarantine is completed to determine if the participant's co-inhabitants did or did not have symptoms or tested positive for COVID-19.

8.4.2 Sub-Study 3:

SARS-CoV-2 testing: Hospital workers will be tested for SARS-CoV-2 virus by RT-PCR every month. This will be a nasopharyngeal swab that will be processed by Quest diagnostics performed during enrollment at one month and two months. This screening NP swab will provide results in EPIC for clinical action within 72 hours. Eligibility criteria to start study medication does not require a negative PCR result to return.

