Asymptomatic PCR+ at baseline: Given the 20% prevalence of asymptomatic coronavirus infection, we will need to screen 250 subjects to accrue the target enrollment of 200 to address the primary endpoint. If the PCR test returns positive while the health care worker is enrolled on the study, the participant will be notified and offered to be removed from the study or to continue with the study medication. Baseline PCR+ subjects who decide to withdraw from the study will be asked to go to occupational health and seek the care of their primary physician. Their study medication will remain blinded and the subject will be asked not to take any additional study medication. For baseline PCR+ subjects who decide to continue on study, they will be asked to keep the daily pill diary. If these subjects are asymptomatic after one week of study medication, they will be asked to return to undergo an on treatment nasopharyngeal swab. If the subject develops symptoms on study medication after 7 days of treatment, the subject will be unblinded. If the subject was assigned to placebo, they will have the option to crossover and get treatment with HCQ 600 mg qd for up to 7 days. Weekly phone calls per the sub-study 3 schedule will continue during this time. AEs will be reported as planned for the study. Baseline PCR+ subjects will be replaced in the prevention study related to the primary objective of sub-study 3 and will not count towards the target accrual or interim analysis. Baseline PCR negative subjects who screen positive at the one month or two-month mark will be considered COVID-19 positive as it relates to the primary endpoint.

Asymptomatic PCR+ at one month: These subjects will count towards the primary endpoint of sub-study 3 as an infection event. Accordingly, they will be unblinded and if on placebo they will be allowed to crossover to HCQ 600 mg qd for 2 weeks. If the subject is assigned to HCQ and turns PCR positive while asymptomatic, the subject will be stopped from study drug and referred to occupational health for standard of care management of health care worker infection. Weekly phone calls will continue. If the subject remains asymptomatic after one month, he/she will return for the one-month swab.

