10.3 Off treatment/Off Study

Each participant has the right to withdraw from the study at any time without prejudice. The investigator may discontinue any person's participation for any reason, including adverse event or failure to comply with the protocol. Should a participant withdraw from the study, the reason(s) must be stated on the case report form, and a final evaluation of the participant should be performed. Reasons for withdrawal include the following:

Progression of Disease: Remove participant from protocol therapy at the time progressive disease is documented. Progression of disease is left to the discretion of the treating physician/ sub-Investigator; however, the following guidelines are provided to help decision making for discontinuing study drug:

Sub-study 1: Progression of disease can be confirmed if there is increase in COVID-19 symptom score for 2 days in a row and is three points higher than baseline. Once criteria for release from quarantine is met in SS1 the patient is off study. Once the person is hospitalized for COVID-19 in sub-study 1 the subject is off study. Participants who have progressive symptoms and are subsequently hospitalized as related to COVID-19 will not be crossed over to receive HCQ at the time of unblinding.

Sub-study 3: Development of new symptomology consistent with COVID-19: e.g. fever, cough, shortness of breath and SARS-COV2 test positivity would lead to unblinding. If on placebo the subject can crossover to HCQ for treatment and stay on study for 14 days or release from quarantine. If the subject was on HCQ the subject is off study and will be instructed to seek medical attention through their primary care physician

Extraordinary Medical Circumstance: If at any time the treating physician feels constraints of this protocol are detrimental to the participant's health remove the participant from protocol therapy.

Participant's refusal to continue treatment: In this event, document the reason(s) for withdrawal.

Failure to comply with protocol (as judged by the investigator such as compliance below 80%, failure to maintain appointments, etc.).

Withdrawal from treatment per patient choice: Patients may withdraw from study treatment at any point in the study for any reason. These subjects are allowed to withdraw from treatment but continue to participate with any of the other study procedures for the intended 2 month period.

Delay in treatment > 7 days due to toxicity

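### Sub-Study 3 has conflicting crossover rules for participants PCR-positive at baseline who continue, and the SAP does not separate adverse events after crossover

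*Protocol*

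**What the plan says.** Section 8.4.2 expects a sizeable group of baseline positives: "Given the 20% prevalence of asymptomatic coronavirus infection, we will need to screen 250 subjects to accrue the target enrollment of 200". They can already be on drug when the result arrives, because "Eligibility criteria to start study medication does not require a negative PCR result to return". They may withdraw, in which case they stay blinded, or continue.

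For those who continue, 8.4.2 says "If the subject develops symptoms on study medication after 7 days of treatment, the subject will be unblinded", and a placebo participant may then take HCQ 600 mg daily for no more than 7 days. For a participant who was negative at baseline and is positive without symptoms at one month, the same section says "Accordingly, they will be unblinded and if on placebo they will be allowed to crossover to HCQ 600 mg qd for 2 weeks"; an HCQ participant in that position stops study drug and the weekly calls go on.

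The general sections read differently:

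- Study Summary: placebo participants may cross over on progression or confirmation of virus.
- Section 6.0: crossover follows a positive PCR, with no symptom condition.
- Section 5.0: "If the participant at any time has worsening symptoms consistent with new onset of COVID-19 disease a COVID-19 PCR test is performed"; if it is positive, the pharmacist discloses the arm and crossover is offered.
- Section 7.5: participants with defined worsening symptoms "but do not require hospitalization and tests positive for SARS-CoV2 virus are allowed to cross over to receive HCQ", and the crossover course is described as 2 weeks.
- Section 10.3: new symptoms such as "fever, cough, shortness of breath and SARS-COV2 test positivity would lead to unblinding". A placebo participant may cross over and remain on study for 14 days or until quarantine ends; an HCQ participant is off study.
- SAP, Randomization process: anyone who becomes positive may be unblinded if the PIs ask in writing.

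**The concern.** A baseline positive who continues fits both the specific rule in 8.4.2 and the general rules elsewhere, and these differ on the trigger, its timing and the length of treatment. No clause says which prevails. Staff working from Section 5.0, 6.0 or 7.5 would find no sign that 8.4.2 treats this group separately. When a participant is unblinded, and how much HCQ a placebo participant receives, could therefore depend on which page was consulted.

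The statistical exposure is in the safety comparison. The SAP's safety set is everyone randomized who took one dose, with no baseline PCR restriction. Protocol Section 12.2 analyses adverse events as counts per subject, with mean counts by group and a rate ratio. Neither document says to which arm an event belongs once a placebo participant is taking HCQ. Analysed as randomized, it counts as a placebo event. If HCQ raises the event rate, that pulls the ratio toward no difference.

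**Working it through.** **The rules side by side (current protocol and SAP only)**

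| Place | Trigger | Length of crossover HCQ | Exempts baseline positives or cites 8.4.2? |
|---|---|---|---|
| Study Summary | Progression or confirmed virus | Not given | No |
| 5.0 | Symptoms at any time, then positive PCR | Not given | No |
| 6.0 | Positive PCR | Not given | No |
| 7.5 | Symptoms, no admission needed, positive test | 2 weeks | No |
| 8.4.2, baseline positive | Symptoms after 7 days of treatment | At most 7 days | This is the specific rule |
| 10.3 | New symptoms and positive test | Not given; 14 days or quarantine release is time on study | No |
| SAP, Randomization process | Any positive, at the PIs' written request | Not covered | No |

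**Three cases: a placebo participant, positive at baseline, who continues**

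1. No symptoms. The Study Summary and 6.0, read literally, allow crossover once the positive result is known. Section 8.4.2 provides none.
2. Symptoms on day 3. Section 5.0 calls for a PCR test and, if it is positive, disclosure of the arm. Section 8.4.2 says nothing about days 1 to 7.
3. Symptoms on day 10. Sections 5.0 and 8.4.2 both lead to unblinding (5.0 after a positive PCR), but 8.4.2 allows at most 7 days of HCQ and 7.5 describes 2 weeks.

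For an HCQ participant in case 3, 8.4.2 does not say whether drug stops, while 10.3 takes the participant off study.

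**Size of the group**

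Inputs: target 200, baseline positivity 20% and 250 screened (8.4.2); allocation "1:1 randomization in each cohort between the arms 1 and 2" (Study Summary).

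- Reproducing the plan's figure: 200 / (1 − 0.20) = 250. It matches.
- Expected baseline positives: 250 × 0.20 = 50.
- On placebo: 50 / 2 = 25, out of 250 / 2 = 125 randomized to placebo, or 25 / 125 = 20%. The denominator of 125 is fair because Section 4.1.2 places randomization before the swab.

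The number who actually cross over needs three shares that the documents do not give: those who continue, those who then have symptoms, and those who accept. The range is therefore 0 to 25.

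**Exposure in dispute, per crossover participant**

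- 7 days: 7 × 600 mg = 4.2 g.
- 14 days: 14 × 600 mg = 8.4 g.
- Difference: 4.2 g, against 56 × 600 mg = 33.6 g for the full 8-week course.

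**Ceiling for all placebo crossover, under any rule**

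Add every placebo infection at the planned 10%: 100 × 0.10 = 10. Then 25 + 10 = 35, and 35 / 125 = 28% if every one of them crossed over; 0 if none did. This is the bound for the adverse-event question, which exists even if the sections agree.

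**The case against.** The best reply is that 8.4.2 is the specific rule, that the amendment log shows handling of asymptomatic positives was clarified on purpose, and that a specific rule governs general ones. Much of this stands.

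A reader might infer that an infected worker without symptoms at one month would, under 5.0, 7.5 and 10.3, stay blinded on assigned drug, against 8.4.2. The documents do not support that. Those sections describe what happens when a symptomatic participant tests positive; none says unblinding happens only then, and none keeps such a person on HCQ. The passages without a symptom condition (Study Summary and 6.0) agree with 8.4.2, and the SAP's wording is permissive.

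Two more readings go too far. The 14 days in 10.3 attaches to staying on study, in text offered as guidance, so it is not a second source for a 14-day course. And the 7 days and 2 weeks within 8.4.2 belong to two different groups, so they do not conflict with each other.

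It is also true that 8.4.2 does not bar unblinding for symptoms in the first 7 days, so case 2 is a gap and not a prohibition.

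What the reply does not reach is cases 1 and 3. There the general sections, by their own terms, cover baseline positives and give a different trigger or duration, with no exemption and no precedence clause.

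**Conclusion.** The concern holds for baseline positives who continue. The current protocol gives them incompatible crossover triggers and durations and leaves days 1 to 7 unaddressed in the rule written for them. For asymptomatic positives at one month there is only a missing cross-reference.

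The group is about 50 people, about 25 on placebo, if the protocol's own 20% is right. A reader might take 50 as the number affected, or assume some percentage of the 25 cross over. Neither is supported: those who withdraw stay blinded, 8.4.2 does not unblind those who remain free of symptoms, and crossover is optional.

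The primary endpoint is little affected. Baseline positives are not evaluable for it and are replaced, and an incident case is already an event when the PCR turns positive. No sample size or power figure changes. The exposure is to participant handling, the blind and the adverse-event rate ratio. The expected direction of the last, toward no difference, assumes that HCQ raises the event rate.

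**What to change.** Reconcile the Study Summary, Sections 5.0, 6.0, 7.5, 8.4.2 and 10.3, and the SAP's Randomization process text, into one Sub-Study 3 table. Its rows would be positive at baseline, positive on study without symptoms, and positive on study with symptoms, each by arm. Each cell states whether and when the participant is unblinded, what happens to study drug, and whether and for how long crossover is offered. The other sections then refer to the table. The clinical content of every cell is for the sponsor to decide.

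Separately, because placebo participants may receive HCQ under every version of the rule, the SAP should report placebo-arm adverse events after crossover on their own and base the between-arm rate ratio on events before crossover, with follow-up time cut at the same point.

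The cost is one table, some cross-references and one extra adverse-event summary, with no new visits or tests. The small downside is slightly less placebo follow-up in the rate ratio.

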Clinical Symptom monitoring: Appropriately delegated and credentialed study team members (as example: CRC) will screen for symptoms 1X per week and if present will document the likely treatment related AEs. Follow up with an appropriately delegated and credentialed physician investigator will be undertaken for assessment and grading of events. Participants will be asked if there have been changes in vision such as distortions of blurred vision. Patients who develop COVID-19 symptoms will be instructed to go to occupational health for nasopharyngeal swab. The rate of conversion to PCR positive in each arm at the 2-month mark will be used to assess the primary endpoint.

Electrocardiogram Recordings: An electrocardiogram (12 lead or 6 lead) will be recorded at baseline prior to the initiation of the study drug. Those participants with an ECG in the last 6 months and no QTc prolonging medications do not need a repeat baseline ECG. One month after starting the study drug a repeat ECG will be performed to confirm excessive QTc prolongation has not occurred. If the QTc has prolonged to >500ms dose reduction as described below will be attempted to achieve a QTc of <500ms. Due to the long half-life of HCQ, study medication can be started before the baseline ECG is read.

Pill diary: Electronic pill diary will be turned in by the participant at the end of the study.

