At each contact with the participant, the appropriately delegated and credentialed study team member must seek information on adverse events by specific questioning and, as appropriate, by examination. Information on all adverse events should be recorded immediately in the source document, and also in the appropriate adverse event module of the case report form (CRF). All clearly related signs, symptoms, and abnormal diagnostic procedures results should be recorded in the source document, though should be grouped under one diagnosis.

All adverse events occurring during the study period must be recorded. Adverse events will be measured and graded in accordance with the CTCAE. The clinical course of each event should be followed until resolution, stabilization, or until it has been determined that the study treatment or participation is not the cause. Serious adverse events that are still ongoing at the end of the study period must be followed up to determine the final outcome. Any serious adverse event that occurs after the study period and is considered to be at least possibly related to the study treatment or study participation should be recorded and reported immediately.

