11.1.1 Serious Adverse Events

Adverse events are classified as serious or non-serious.

A serious adverse event is any AE that is:

- fatal
- life-threatening
- requires or prolongs hospital stay
- results in persistent or significant disability or incapacity
- a congenital anomaly or birth defect
- Suspected transmission of an infectious agent (eg, pathogenic or nonpathogenic) via the study drug is an

The PATCH Trial
SAE.

- an important medical event

Important medical events are those that may not be immediately life threatening, but are clearly of major clinical significance. They may jeopardize the participant, and may require intervention to prevent one of the other serious outcomes noted above. For example, drug overdose or abuse, a seizure that did not result in in-patient hospitalization, or intensive treatment of bronchospasm in an emergency department would typically be considered serious. Theft, sale, or use of the study product by any person other than the participant will be reported as a medically important event.

ADVERSE EVENT COLLECTION AND REPORTING INFORMATION:

- All Serious Adverse Events (SAEs) that occur following the participant's written consent to participate in the study must be reported, whether related or not related to study drug. If applicable, SAEs must be collected that relate to any later protocol-specified procedure.
- Following the participant's written consent to participate in the study, all SAEs, whether related or not related to study drug, are collected, including those thought to be associated with protocol-specified procedures. The investigator-sponsor should report any SAE occurring after these aforementioned time periods, which is believed to be related to study drug or protocol-specified procedure.
- An SAE report should be completed for any event where doubt exists regarding its seriousness;
- If the investigator believes that an SAE is not related to study drug, but is potentially related to the conditions of the study (such as withdrawal of previous therapy or a complication of a study procedure), the relationship should be specified in the narrative section of the SAE ReportForm.

All SAEs should be followed to resolution or stabilization.

Adverse events can be spontaneously reported or elicited during open-ended questioning, examination, or evaluation of a participant. (In order to prevent reporting bias, participants should not be questioned regarding the specific occurrence of one or more AEs.)

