11.2 Assessment of Adverse Events

All AEs and SAEs whether volunteered by the participant, discovered by study personnel during questioning, or detected through physical examination, laboratory test, or other means will be reported appropriately. Each reported AE or SAE will be described by its duration (i.e., start and end dates), regulatory seriousness criteria if applicable, suspected relationship to the study drug (see following guidance), and actions taken. To ensure consistency of AE and SAE causality assessments, only the PI or physician sub-investigators may grade AEs, and investigators should apply the following general guideline:

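### Sub-Study 3 weekly calls: the instruction to document likely treatment-related adverse events conflicts with the all-events rule and puts a first causality judgement ahead of physician review

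*Protocol*

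**What the plan says.** **Recording.** Protocol 8.4.2 (Sub-Study 3, Clinical Symptom monitoring) has a delegated team member, with a research coordinator as the example, who "will screen for symptoms 1X per week and if present will document the likely treatment related AEs". The next sentence adds a physician step: "Follow up with an appropriately delegated and credentialed physician investigator will be undertaken for assessment and grading of events". Protocol 11.1 states the general rule, which the SAP repeats under Recording of Adverse Events: "All adverse events occurring during the study period must be recorded".

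**Who judges.** Protocol 11.2 says that "only the PI or physician sub-investigators may grade AEs", and gives consistent causality assessment as the reason.

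**Questioning.** Protocol 11.1 and the SAP say that at each contact staff "must seek information on adverse events by specific questioning and, as appropriate, by examination". Protocol 11.1.1 says in a parenthesis that "participants should not be questioned regarding the specific occurrence of one or more AEs". Protocol 8.4.2 includes a named question: "Participants will be asked if there have been changes in vision such as distortions of blurred vision".

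**Endpoint and analysis.** The Sub-Study 3 secondary objective is the rate of treatment-related adverse events. The SAP (Secondary Objectives) describes it as patient-reported and obtained in the weekly telephone calls. Protocol 12.2 plans a count of adverse events per subject, a mean by group and a rate ratio, with no restriction to related events. The SAP's analysis-set table likewise lists adverse events without that restriction.

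**The concern.** The weekly call is the named source of the secondary safety endpoint. If the caller follows 8.4.2 as written, an event judged unlikely to be drug-related may not be written down, and the physician can assess only what has been written down. In a placebo-controlled trial, the comparison that depends least on anyone's opinion of cause is all recorded events by arm. A relatedness judgement made before recording weakens that comparison. It also means that the related-event count reflects two judgements, the caller's and then the physician's, with only the second specified.

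The questioning rules matter because elicited and volunteered reports give different counts. If callers choose differently among three instructions, the event count depends partly on who made the call.

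**Working it through.** The plan states no figure that can be reproduced here. It gives no adverse event rate and no expected share judged related. The check is therefore a comparison of texts, followed by an illustration that rests on assumed rates.

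**1. Recording rules.** Section 8.4.2 names events likely to be treatment related. Section 11.1 and the SAP name all events, and 11.0 defines an adverse event without requiring a causal link. A caller who does no more than 8.4.2 asks falls short of 11.1.

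**2. Path to the endpoint.** The order is call, documentation, physician assessment, count by arm. Section 8.4.2 puts a causality judgement at the second stage, while 11.2 places causality at the third. One ground for relatedness in 11.2.1 is that the event abates on stopping or reducing the drug, which may not be known at the time of the call.

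**3. Relatedness scales.**

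| Place | Wording of relatedness |
|---|---|
| 8.4.2, weekly call | likely |
| 8.5, dose reduction | possibly, probably or definitely |
| 11.2.1 and 11.2.2 | yes or no |

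An event that a physician would call possibly related could fall below the caller's threshold of likely. These sections need to be reconciled.

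**4. Questioning rules.** Section 11.1 and the SAP ask for specific questioning, 11.1.1 advises against asking about specific events, and 8.4.2 names vision. Read literally, the vision question does not satisfy 11.1.1. The SAP carries only the first of these rules.

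**5. Illustration (all rates assumed).** Let b be background events per subject in both arms, d the drug-caused events per subject on HCQ, f the share of background events documented, and s the share of drug-caused events documented. With 100 subjects per arm and Poisson counts:

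- rate ratio = (f·b + s·d) / (f·b)
- SE of the log rate ratio = √[1/(100(f·b + s·d)) + 1/(100·f·b)]

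With b = 1.0 and d = 0.5:

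| s | f | Expected events, HCQ / placebo | Rate ratio | SE |
|---|---|---|---|---|
| 1.0 | 1.0 | 150 / 100 | 1.50 | 0.129 |
| 0.5 | 0.5 | 75 / 50 | 1.50 | 0.183 |
| 0.8 | 0.5 | 90 / 50 | 1.80 | 0.176 |
| 0.8 | 0.2 | 60 / 20 | 3.00 | 0.258 |
| 0.2 | 0.5 | 60 / 50 | 1.20 | 0.191 |

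The last row represents callers who miss drug effects they do not expect: (0.5×1.0 + 0.2×0.5)/(0.5×1.0) = 0.60/0.50 = 1.20, with SE √(1/60 + 1/50) = 0.191.

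Equal capture leaves the ratio alone and costs precision. Unequal capture changes the ratio, upwards if background events are dropped more often and downwards if drug-caused events are. The baseline assumption also matters: with d = 0.5 and b running from 0.5 to 2.0, the all-event ratio runs from 2.00 to 1.25, and the row with s = 0.8 and f = 0.2 runs from 5.00 to 2.00. Nothing in the documents selects a row.

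**The case against.** The strongest reply is that one loosely worded sentence sits under an explicit general rule. Section 11.1 applies at each contact and requires information on all events to be recorded, the SAP repeats it, and 11.2 says that events found by any means are to be reported. A caller who follows 11.1 loses nothing. Physician assessment and grading come in the very next sentence of 8.4.2, and the coordinator is only an example of who may call. The endpoint is itself limited to treatment-related events, so some relatedness judgement belongs in it. Section 11.1.1 collects all serious events after consent regardless of relatedness. Checks repeat weekly and again at two months, so a persisting event can be picked up later. On questioning, 11.1.1 is a parenthetical should-not, specific questioning can mean actively asking about events, and the vision question can be read as a targeted exception tied to the protocol's retinal concern.

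Most of this stands, and it limits the point. A reader might infer that the calls record related events alone, or that coordinators control what enters the safety data. The documents do not support either reading: 8.4.2 contains no word of exclusion, 11.1 points the other way, and the physician step exists. A reader might also infer that any loss would fall mainly on unexpected toxicities, or put a percentage on the lost precision. Neither has a basis in the documents. A formula based only on the share of events kept assumes equal capture in both arms, which contradicts a claim of selective loss. A larger standard error need not weaken the comparison either: in the illustration, ln(1.50)/0.129 is about 3.14 for all events, while the row with s = 0.8 and f = 0.5 gives about 3.33.

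The reply does not remove the conflict. Two current instructions tell the same caller different things, and physician follow-up cannot reach an event that was never documented.

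**Conclusion.** The point holds as an internal inconsistency that bears on the secondary safety endpoint. Section 8.4.2 conflicts with 11.1 and the SAP on what is recorded, and it places a first causality judgement with a caller who may not be a physician, against the purpose stated in 11.2. What is at risk is non-serious events that the caller leaves out, and only to the extent that callers follow 8.4.2 rather than 11.1. Serious events are covered. The size and direction of any effect cannot be determined from the documents; the rate ratios above rest wholly on assumed rates and show only that both precision and the estimate could move. The questioning conflict is real on a literal reading and milder on a generous one. The primary infection endpoint is not affected. The wording should be corrected, because the change is cheap and an undocumented short-lived event may not be recoverable.

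**What to change.** - **Recording.** In 8.4.2, have the weekly caller document all adverse events, in line with 11.1 and the SAP.
- **Attribution.** Have a physician assign relatedness afterwards, on one scale used throughout the protocol. The physician should be blinded where possible. It will not always be possible: under 7.5 the coordinator and clinical investigator learn that a participant was on placebo after a positive test, and under 8.4.2 weekly calls continue after unblinding of asymptomatic positives at one month.
- **Analysis.** State in 12.2 and in the SAP that all adverse events are compared by arm, with treatment-related events as a subset. Section 12.2 already plans an unrestricted count, so this mainly settles which count answers the secondary objective.
- **Questioning.** Reconcile 8.4.2, 11.1, 11.1.1 and the SAP into one script used in both arms: an open question plus the vision question already required.

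The cost is amended wording in both documents, a short call script and more event entries per call. No change to sample size, visits or the primary analysis is needed.
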